8.6 ADVERSE EVENTS AND SERIOUS ADVERSE EVENTS

8.6.1 DEFINITION OF ADVERSE EVENTS

For this protocol, an AE is any untoward medical occurrence (eg, sign, symptom, disease, syndrome, intercurrent illness, CS abnormal laboratory finding, injury, or accident) that emerges or worsens following administration of the study drug and until the EOS participation. The untoward medical occurrence may not necessarily have a causal relationship to the administration of the IP. An AE can therefore be any unfavorable and/or unintended sign (including a CS abnormal laboratory result), symptom, or disease temporally associated with the use of a medicinal (investigational) product, whether or not related to the medicinal (investigational) product. A treatment-emergent AE is one that occurs after any exposure to treatment.

A pre-existing condition is one that is present prior to the start of the study and is to be reported as part of the subject's medical history. It should be reported as an AE only if the frequency, intensity, or the character of the condition worsens during the study.

Any CS change in the study safety evaluations, (eg, vital signs, physical/neurological examinations, etc.) post injection must be reported as an AE.

For each laboratory test result outside the reference range, the Investigator must ascertain if the abnormal lab result is a CS result for that individual subject. This determination, however, does not necessarily need to be made the first time an abnormal value is observed; the Investigator may repeat

the laboratory test or request additional tests to verify the results of the original laboratory test. If a laboratory value is determined to be a CS result for a subject, this may be considered an AE.

8.6.2 DEFINITION OF SERIOUS ADVERSE EVENTS

A SAE includes any event that results in any of the following outcomes:

- Death
- Life-threatening (ie, the subject was, in the opinion of the Investigator, at immediate risk of death from the event as it occurred. It does not apply to an AE that hypothetically might have caused death if it were more severe.)
- Persistent or significant disability/incapacity or substantial disruption of the subject's ability to carry out normal life functions
- Requires in-patient hospitalization or prolongs hospitalization (ie, a prolonged hospitalization beyond the expected length of stay; hospitalizations for elective medical/surgical procedures, scheduled treatments, or routine check-ups are not SAEs by this criterion)
- Congenital anomaly/birth defect (ie, an adverse outcome in a child or fetus of a subject exposed to the molecule or IP before conception or during pregnancy)
- Does not meet any of the above serious criteria but based upon appropriate medical judgment may
 jeopardize the subject or may require medical or surgical intervention to prevent one of the
 outcomes listed above (ie, is a significant or important medical event)

8.6.3 CLASSIFICATION OF AN ADVERSE EVENT

8.6.3.1 SEVERITY OF EVENT

The Investigator is responsible for evaluating all AEs and determining the severity of the event. Severity will be categorized as mild, moderate, or severe according to the following definitions:

- **Mild:** Event may be noticeable to subject; does not influence daily activities; usually does not require intervention.
- Moderate: Event may be of sufficient severity to make a subject uncomfortable; performance of daily activities may be influenced; intervention may be needed.
- **Severe:** Event may cause severe discomfort; usually interferes with daily activities; subject may not be able to continue in the study; treatment or other intervention usually needed.

8.6.3.2 RELATIONSHIP TO STUDY INTERVENTION

Relationship of an AE to IP will be assessed as follows:

• **Definite:** There is a clinically plausible time sequence between the onset of the AE and the administration of IP when the event responds to withdrawal of IP and recurs with readministration of IP.

- Related: There is a clinically plausible time sequence between the onset of the AE and the
 administration of IP; the AE is unlikely to be caused by the concurrent/underlying illness, other
 drugs or procedures.
- **Possibly Related:** There may or may not be a clinically plausible time sequence between the onset of the AE and the administration of IP and a cause cannot be ruled out.
- **Unrelated:** There is not a temporal or causal relationship to IP administration.

8.6.3.3 EXPECTEDNESS

The PI/designee will be responsible for determining whether an AE is expected or unexpected. An unexpected AE is one not identified in nature, severity, or frequency in the current protocol or IB.

8.5.4 TIME PERIOD AND FREQUENCY FOR EVENT ASSESSMENT AND FOLLOW-UP

SAEs that are identified on the last scheduled contact must be recorded on the AE eCRF page and reported to the Sponsor or the authorized representative according to the reporting procedures outlined in Section 8.6.6. This may include unresolved previously reported SAEs, or new SAEs. The Investigator should follow these SAEs until the events are resolved, or the subject is lost to follow-up. The Investigator should continue to report any significant follow-up information to the Sponsor or the authorized representative, and the IRB, up to the point the event has been resolved. Resolution means the subject has returned to the baseline state of health, or the Investigator does not expect any further improvement or worsening of the subject's condition.

Any new SAEs reported by the subject to the Investigator that occur after the last scheduled contact and are determined by the Investigator to be reasonably associated with the administration of IP should be reported to the Sponsor or the authorized representative, and the IRB, as required.

8.6.5 ADVERSE EVENT REPORTING

The Investigator will assess subjects at each study visit and posttreatment per protocol for the occurrence of AEs. In order to avoid bias in eliciting AEs, subjects should be asked the following nonleading question: "How have you felt since your last visit?" All AEs (serious and non-serious) reported by the subject must be recorded on the source documents and eCRFs.

Adverse Events will be recorded beginning from the time of consent. Adverse Events that occur prior to dosing will also be noted in the medical history.

8.6.6 SERIOUS ADVERSE EVENT REPORTING

The Investigator will report any SAE to the pharmacovigilance within 24 hours of being made aware of it, whether or not considered study intervention related, including those listed

in the protocol or IB and must include an assessment of whether there is a reasonable possibility that the study intervention caused the event. Study endpoints that are serious adverse events (eg, all-cause mortality) must be reported in accordance with the protocol unless there is evidence suggesting a causal relationship between the study intervention and the event (eg, death from anaphylaxis). In that case, the Investigator must report the event to the Sponsor in the shortest possible time.

All SAEs will be followed until satisfactory resolution or until the study center Investigator deems the event to be chronic or the participant is stable. Other supporting documentation of the event may be requested by the local or centralized IRB and study Sponsor and should be provided as soon as possible.

The study Sponsor will be responsible for notifying the Food and Drug Administration (FDA) of any unexpected fatal or life-threatening suspected adverse reaction as soon as possible, but in no case later than 7 calendar days after the Sponsor's initial receipt of the information and in compliance with the 15 day requirement. In addition, the Sponsor must notify FDA and all participating Investigators in an IND safety report of potential serious risks, from clinical trials or any other source, as soon as possible, but in no case later than 15 calendar days after the Sponsor determines that the information qualifies for reporting.

8.6.7 REPORTING EVENTS TO PARTICIPANTS

The Sponsor will disclose clinical trial data to individuals, to Investigators at sites, and publicly as aggregate summaries, in accordance with applicable regulations and requirements.

8.6.8 EVENTS OF SPECIAL INTEREST

Not applicable.

8.6.9 REPORTING OF PREGNANCY

During the trial, all WOCBP should be instructed to contact the Investigator immediately (within 24 hours) if they suspect they might be pregnant (eg, missed or late menstrual cycle). The Investigator must immediately notify

Pharmacovigilance of any female subject who becomes pregnant any time during study participation, record the information on the Pregnancy Notification Form and send the form to the authorized representative. The study center will be asked to follow-up with the subject periodically during the pregnancy for ongoing health and safety information through term, as applicable. Subjects who become pregnant during the study will be discontinued.

In the case of male subject's female partner becoming pregnant while the male subject is in this study, the Investigator should attempt to collect pregnancy information on the male subject's female partner. This applies only to male subjects who receive study treatment.

The Investigator will record pregnancy information on the appropriate pregnancy form and submit it to the sponsor within 24 hours of learning of the partner's pregnancy. The female partner will also be followed to determine the outcome of the pregnancy. Information on the status of the mother and child will be forwarded to the sponsor. Generally, the follow-up will be no longer than 6 to 8 weeks following

the estimated delivery date. Any termination of the pregnancy will be reported regardless of fetal status (presence or absence of anomalies) or indication for the procedure.

8.7 UNANTICIPATED PROBLEMS

8.7.1 DEFINITION OF UNANTICIPATED PROBLEMS

The Office for Human Research Protections (OHRP) considers unanticipated problems involving risks to participants or others to include, in general, any incident, experience, or outcome that meets all of the following criteria:

- Unexpected in terms of nature, severity, or frequency given (a) the research procedures that are
 described in the protocol-related documents, such as the IRB-approved research protocol and
 informed consent document; and (b) the characteristics of the participant population being
 studied;
- Related or possibly related to participation in the research ("possibly related" means there is a
 reasonable possibility that the incident, experience, or outcome may have been caused by the
 procedures involved in the research); and
- Suggests that the research places participants or others at a greater risk of harm (including physical, psychological, economic, or social harm) than was previously known or recognized.

8.7.2 UNANTICIPATED PROBLEM REPORTING

The Investigator will report unanticipated problems (UPs) to the reviewing IRB and to the Data Coordinating Center (DCC)/lead PI. The UP report will include the following information:

- Protocol identifying information: protocol title and number, Pl's name, and the IRB project number;
- A detailed description of the event, incident, experience, or outcome;
- An explanation of the basis for determining that the event, incident, experience, or outcome represents an UP;
- A description of any changes to the protocol or other corrective actions that have been taken or are proposed in response to the UP.

To satisfy the requirement for prompt reporting, UPs will be reported using the following timeline:

- UPs that are SAEs will be reported to the IRB and to the DCC/study Sponsor within 24 hours of the Investigator becoming aware of the event.
- Any other UP will be reported to the IRB and to the DCC/study Sponsor within <7 days of the Investigator becoming aware of the problem.

• All UPs should be reported to appropriate institutional officials (as required by an institution's written reporting procedures), and the supporting agency head (or designee) within 14 days of the IRB's receipt of the report of the problem from the Investigator.

8.7.3 REPORTING UNANTICIPATED PROBLEMS TO PARTICIPANTS

The Sponsor will disclose clinical trial data to individuals, to Investigators at sites, and publicly as aggregate summaries, in accordance with applicable regulations and requirements.

9 STATISTICAL CONSIDERATIONS

9.1 STATISTICAL HYPOTHESES

The primary objective of this study is to evaluate the efficacy of etokimab compared to placebo in the treatment of subjects with CRSwNP following a 16-week treatment period (change from baseline using co-primary endpoints). The hypotheses for the co-primary efficacy endpoints are delineated below.

Co-Primary Efficacy Endpoints:

Statistical hypotheses associated with the co-primary efficacy endpoints are as follows:

- Treatment of adults diagnosed with CRSwNP using etokimab will result in a significantly greater reduction of Week 16 NPS from baseline when compared to placebo, and
- Treatment of adults diagnosed with CRSwNP using etokimab will result in a significantly greater reduction of Week 16 SNOT-22 score from baseline when compared to placebo

9.2 SAMPLE SIZE DETERMINATION

Sample size estimates were calculated based on the following assumptions:

- Overall alpha=0.05
- Co-primary endpoints
- Hierarchical testing of the 2 active treatment arms versus placebo
- At least 85% power to detect a clinically meaningful difference between etokimab and placebo

Based on data from similar trials conducted in adult subjects with CRSwNP, a difference in NPS of 1.3 between the etokimab change from Baseline to Week 16 and the placebo group change from Baseline to Week 16 will be clinically meaningful (*Bachert et al. 2016*). Assuming a standard deviation (SD) of 1.5, and a significance level of 5%, a sample size of n=27 for each treatment arm will provide approximately 87% power to detect the stipulated difference. In order to account for the dilution of treatment effect due to 18% dropouts and missing data, approximately 33 subjects are planned to be randomized equally to each of the 3 treatment arms.

The second co-primary endpoint is SNOT-22 total score. In a trial of adults with CRSwNP, the difference in mean change from Baseline to Week 16 between active and placebo was 18.1. Assuming a common standard deviation of 19.2, and 2-sided significance level of 5%, the sample size of 27 subjects provides 92% power to detect the stipulated treatment difference. Hence, adjusting for 18% dropouts and missing data, n=33 subjects will provide >85% desired power to detect a clinically meaningful difference in this endpoint between each active arm and placebo.

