Abbreviations: ANCOVA = analysis of covariance, CT = computed tomography, EOT = end of treatment, EQ-5D = EuroQoL-5D Scale, MMRM = mixed effects model with repeated measures, MPS = mental component summary, NPIF = nasal peak inspiratory flow, NPS = Nasal Polyp Score, PCS = physical component summary, SF-36 = Short Form 36 Health Survey, SNOT-22 = Sino-Nasal Outcome Test, UPSIT = University of Pennsylvania Smell Identification Test, VMSOD = volumetric maxillary sinus occupied by disease

Statistical significance for the co-primary efficacy endpoints will be declared if both p-values for the tests of the individual hypotheses, as described below, are < 0.05.

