9.4.2.1.1 FIRST CO-PRIMARY ENDPOINT

The first co-primary endpoint is the change from Baseline to Week 16 in bilateral endoscopic NPS while on treatment.

Baseline endoscopic NPS is the sum of the left and right nasal polyposis score at the randomization visit. The NPS is also measured every 4 weeks during treatment and at end of treatment (Week 16). A general linear MMRM using change from baseline in NPS scores at Weeks 4, 8, 12, and 16 as response, stratification factor, treatment group as fixed effect (3 levels), treatment by stratification factor, and treatment by time interaction as fixed effects, Baseline (Day 1) NPS score as fixed continuous covariate, and subject as a random effect, will be used to obtain least squares means at EOT, to compare the etokimab treatment arms with the placebo arm.

No imputation of data for missing data due to treatment discontinuation will be implemented in the primary analysis. Comparison of the treatment arms will be based on the Week 16 least squares means of the treatment arms. An unstructured covariance matrix will be assumed and estimated in order to obtain associated standard errors for least squares means and to carry out the treatment comparisons. In case of convergence problems for the maximum likelihood estimates, other covariance structures with fewer parameters may be sought from the range of options provided in SAS PROCEDURE MIXED.

Comparison of each treatment arm with placebo will be based on the Week 16 least squares means obtained from the MMRM, where missing data due to treatment discontinuation are regarded as missing at random. Testing will be conducted in a hierarchical manner such that the comparison of the etokimab every 4 weeks treatment arm versus placebo will be conducted first. If the results of the comparison of the etokimab every 4 weeks treatment arm versus placebo are statistically significant, the etokimab every 8 weeks treatment arm will be compared to placebo. The p-value for the comparison will be obtained and compared to the significance level of 5%. An associated 2-sided 95% confidence interval will be obtained for the active minus placebo change from baseline to week 16 in the NPS for each treatment arm tested. No further adjustment will be made for testing each dosing regimen with placebo.

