9.4.2.1.2 SECOND CO-PRIMARY ENDPOINT

The second co-primary endpoint is the change from Baseline to Week 16 in SNOT-22 scores.

An MMRM as described above for NPS, using the Baseline (Day 1) SNOT-22 score as fixed covariate, will be utilized for the SNOT-22.

Baseline endoscopic NPS is the sum of the left and right nasal polyposis score at the randomization visit.

Comparison of each treatment arm with placebo will be based on the Week 16 least squares means obtained from the MMRM. The p-value for the comparison will be obtained and compared to the significance level of 5%. An associated 2-sided 95% CI will be obtained for the active minus placebo change from baseline to Week 16 in the SNOT-22. No further adjustment will be made for testing each dosing regimen with placebo.

In order to assess the impact of missing data due to treatment discontinuation, a sensitivity analysis may be performed where their data after treatment discontinuation will be imputed using multiple imputation and the statistical analysis using MMRM will be repeated. Another sensitivity analysis may be performed where observed values of the SNOT-22 score obtained during study but after treatment discontinuation, if available, will be used. The MMRM model will be utilized where the treatment discontinuations are regarded as NMAR. Full details will be specified in the SAP.

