8.1. Primary Efficacy Endpoint and Analysis

Statistical hypotheses associated with the co-primary efficacy endpoints are as follows:

- Treatment of adults diagnosed with CRSwNP using etokimab will result in a significantly greater reduction of Week 16 NPS from baseline when compared to placebo, and
- Treatment of adults diagnosed with CRSwNP using etokimab will result in a significantly greater reduction of Week 16 SNOT-22 score from baseline when compared to placebo

Statistical significance for the co-primary efficacy endpoints will be declared if and only if both 2-sided pvalues for the tests of the individual hypotheses are < 0.05. Testing will be conducted in a hierarchical manner for each co-primary endpoint such that the comparison of the etokimab Q4W treatment arm versus placebo will be conducted first. If the result from this test is statistically significant, then the comparison of the etokimab Q8W treatment arm versus placebo will be performed. If the result from the etokimab Q4W versus placebo is not statistically significant, no further testing will be performed for the etokimab Q8W treatment arm versus placebo.

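### Protocol 9.2 states 85% power without scope: the figure is per endpoint and per comparison, the SAP gives about 80% for the both-endpoints rule, and neither document says Q8W power is lower because Q8W is tested second

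*Protocol*

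**What the plan says.** Protocol 9.2 gives its planning assumptions as a list: overall alpha 0.05, co-primary endpoints, hierarchical testing of the two active arms, and "At least 85% power to detect a clinically meaningful difference between etokimab and placebo". The text below the list gives about 87% power for NPS and 92% for SNOT-22 with 27 subjects per arm. After allowing for 18% dropout and missing data, "approximately 33 subjects are planned to be randomized equally to each of the 3 treatment arms". The SNOT-22 paragraph ends by saying that "n=33 subjects will provide >85% desired power to detect a clinically meaningful difference in this endpoint between each active arm and placebo".

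The decision rule is stricter than any one of these tests. Protocol 9.4.2 says significance for the co-primary endpoints is "declared if both p-values for the tests of the individual hypotheses, as described below, are < 0.05". Protocol 9.4.2.1.1 adds that "the comparison of the etokimab every 4 weeks treatment arm versus placebo will be conducted first". SAP 8.1 states the order more broadly: "Testing will be conducted in a hierarchical manner for each co-primary endpoint", and "If the result from the etokimab Q4W versus placebo is not statistically significant, no further testing will be performed for the etokimab Q8W" comparison with placebo.

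SAP 3.6 repeats the protocol's list without the 85% item. It adds that combined power for both endpoints is about 80% if the endpoints are not negatively correlated. It does not name a regimen.

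The protocol synopsis describes the roughly 33 per arm as evaluable, within a total of about 100 enrolled.

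**The concern.** An unscoped 85% that sits beside the co-primary and hierarchical features reads as power for the design with those features. It is power for a single test. Someone with only the protocol would expect 85% for the both-endpoints rule, where the SAP says about 80%.

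The gap is larger for Q8W, which can be declared only if Q4W has already succeeded. Neither document says that this lowers Q8W power. A Q8W result that is non-significant or never tested could then be given more weight than it deserves. That matters because the trial compares two regimens and is meant to inform later development.

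The synopsis wording adds a second mismatch, on whether 33 is the number randomized or the number expected to contribute data.

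**Working it through.** **Inputs from Protocol 9.2 and SAP 3.6.** NPS difference 1.3, SD 1.5; SNOT-22 difference 18.1, SD 19.2; two-sided 5%; 27 per arm after 18% loss. Randomization is 1:1:1, so both active arms share one placebo arm, and with equal arm sizes the two treatment contrasts correlate 0.5.

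**Inputs not in the documents (assumed).** Correlation between the two endpoints, 0 to 0.5. Q8W effect equal to the Q4W effect.

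**Step 1: reproduce the stated figures.** Two-sample t-test, noncentrality = difference / (SD × √(2/n)).
- NPS: 1.3 / (1.5 × √(2/27)) = 3.18; power 87.8% (stated 87%).
- SNOT-22: 18.1 / (19.2 × √(2/27)) = 3.46; power 92.5% (stated 92%).
- Inflation: 27 / 0.82 = 32.9, so 33 randomized per arm.
- Both endpoints at zero correlation: 0.87 × 0.92 = 80.0% from the stated figures, or 81.2% unrounded (SAP: about 80%).

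All of the documents' figures reproduce.

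**Step 2: the sequence.** Q4W succeeds if both of its tests pass. With SAP 8.1's order applied to each endpoint, Q8W succeeds on both only if all four tests pass. A four-variate normal calculation uses correlation 0.5 between regimens and ρ between endpoints:

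| ρ | Q4W, both endpoints | Q8W, all four tests | Difference |
|---|---|---|---|
| 0 | 81.2% | 69.6% | 11.6 points |
| 0.3 | 82.3% | 71.5% | 10.8 points |
| 0.5 | 83.3% | 73.0% | 10.3 points |

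Simulated t-tests (200,000 trials per cell, with two-arm or three-arm pooled variance) give 81.0–83.9% for Q4W and 69.5–74.0% for Q8W. On this basis Q4W joint power reaches 85% only at ρ of about 0.75 or more.

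**Step 3: what the sequence costs Q8W.** With equal effects, Q8W without the sequence would have the same joint power as Q4W, so the difference column is the net cost: about 10–12 points. At ρ = 0, Q4W fails in 100 − 81.2 = 18.8% of trials. In 11.6% Q8W would have passed on its own tests; in the other 7.2% it would have failed as well. At ρ = 0.5 the split is 10.3% and 6.4%.

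**Step 4: sensitivity to the analysis.** The planned repeated-measures model uses partial data and adjusts for baseline. The ranges below cover ρ from 0 to 0.5 and both variance choices. The effective n and the baseline correlations are assumed.

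| Basis | Q4W, both | Q8W, all four |
|---|---|---|
| 27 per arm, unadjusted | 81.0–83.9% | 69.5–74.0% |
| 27, baseline–change correlation 0.2 | 83.2–85.6% | 72.4–76.5% |
| 27, baseline–change correlation 0.3 | 85.7–87.6% | 76.2–79.5% |
| Effective 30 per arm | 86.4–88.1% | 77.3–80.2% |
| All 33 contributing fully | 90.1–91.3% | 83.0–85.2% |

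Q8W is lower than Q4W in every row.

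**Step 5: the synopsis.** 33 × 0.82 = 27.1, so 33 randomized leaves about 27. To have 33 left after 18% loss would need 33 / 0.82 = 40.2, about 40 per arm or 120 in total. The synopsis plans about 100, and 3 × 33 = 99. So 33 can only be the randomized number.

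**The case against.** The strongest reply is that nothing is miscalculated. Protocol 9.2 reports each endpoint separately, its SNOT-22 sentence limits the claim to that endpoint and to each active arm against placebo, and SAP 3.6 already gives the both-endpoints power with its correlation condition. That stands. This is a matter of scope and an omitted statement, not faulty arithmetic. But the list item itself carries no such limit, and SAP 3.6 is silent on the effect of testing Q8W second.

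A reader might infer that joint power for Q4W is shown to be below 85%. The documents do not support that. Twenty-seven complete cases is the conservative end, because the planned model uses all available data and a baseline covariate. Step 4 shows that Q4W joint power could exceed 85%.

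A reader might also take the SAP's 80% as a stated Q4W figure. SAP 3.6 names no regimen. The figure is joint power for one regimen against placebo before any sequence, so it is final only for Q4W, which is tested first.

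Finally, a reader might charge all of Q4W's 16–19% failure probability to Q8W as a cost of the sequence. About 6 to 7 points of that are trials in which Q8W would have failed on its own tests, so the net cost is 10–12 points.

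**Conclusion.** The point holds as a minor correction. The 85% in Protocol 9.2 is supported for each endpoint in each active-versus-placebo comparison. The protocol omits the SAP's figure of about 80% for the rule actually used, and neither document says that Q8W power is lower.

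With 27 completers per arm, a Q8W effect equal to Q4W, endpoint correlation 0 to 0.5, and SAP 8.1's order on both endpoints, joint power is about 81–84% for Q4W and 70–74% for Q8W. The effect and correlation assumptions are not in the documents, and a smaller Q8W effect would lower its figure. Protocol 9.4.2.1.2 does not repeat the order for SNOT-22. If the order applied to NPS alone, Q8W would be about 74–77%.

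The synopsis conflicts with 9.2 on what 33 per arm means. None of this shows the trial to be too small or the decision rule to be invalid.

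**What to change.** 1. **Protocol 9.2.** Limit the 85% item to each co-primary endpoint in each active-versus-placebo comparison. Add the SAP 3.6 figure: about 80% for both endpoints together, assuming no negative correlation, before the testing sequence is applied.
2. **Protocol 9.2 and SAP 3.6.** State that Q8W power is lower because Q8W is tested only after Q4W succeeds. Give a figure computed on one consistent basis with its assumptions named, for example about 70–74% with 27 completers per arm, equal effects and endpoint correlation 0 to 0.5.
3. **Synopsis.** Replace the evaluable count with about 33 randomized per arm, of whom 27 are expected to remain after 18% loss.

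The cost is wording only. Patients, alpha, tests and decision rule do not change. The protocol edits can go with the next amendment under Protocol 10.2.2.
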